### **7.2.6 *Medical History***

Medical history will be collected at Screening. Data will be listed by treatment for the Safety Population. Medical/surgical history will be coded using the Medical Dictionary for Regulatory Activities (MedDRA) version 21.0.

### **7.2.7 *Protocol Deviations***

Subjects with protocol deviations will be listed by treatment for all subjects in the Safety Population.

### **7.2.8 *Informed Consent***

Informed consent will be collected before screening or first thing in screening visit. Date of informed consent will be listed by treatment for the Safety Population. By subject listing, corresponding analysis set will also be provided.

## **7.3 Pharmacokinetic Analysis**

### **7.3.1 *Handling Missing or Non-Quantifiable Data***

Concentrations below the lower limit of quantitation (LLOQ) before the first measurable concentration will be assigned a value of zero. Any LLOQ values between measurable concentrations in a profile will be set to missing in the derivation of PK parameters, concentration summary, and the individual subject plots. Concentrations below the LLOQ which occur after the last measurable concentration will be set to missing in the derivation of PK parameters and in the individual subject plots but will be set as zero for the plasma concentration summary.

### **7.3.2 *Pharmacokinetic Concentrations***

Individual plasma concentrations of OP-101 will be listed by treatment at each time point. Plasma concentration of OP-101 will also be summarized by treatment at each nominal time based on PK Concentration Population. Mean concentrations of plasma OP-101 will be plotted on a linear and semi-logarithmic scale versus nominal time points by treatment. Individual plasma concentrations of OP-101 will be plotted on a linear and semi-log scale versus actual

sampling time points by treatment. The spaghetti plots of individual plasma OP-101 concentration on linear and semi-Log scale will also be presented.

Blood samples for PK analysis can be obtained within  $\pm 5$  minutes of the scheduled sampling time for sample times  $\leq 1$  hour, within  $\pm 10$  minutes of the scheduled sampling time for sample times  $\leq 12$  hours, and within  $\pm 2$  hours of the scheduled sampling times for sample times  $> 12$  hours. Actual sampling times that are outside the sampling window will be listed but excluded from summary statistics.

Urine PK samples will be collected within 60 to 30 minutes prior to dosing (spot sample) and between 0 to 4, 4 to 8, 8 to 12, 12 to 18, 18 to 24, and 24 to 48 hours after dosing. Urine concentrations and volumes will be listed and summarized by treatment and nominal time interval.

### ***7.3.3 Pharmacokinetic Parameters Calculation***

Standard non-compartmental methods (NCA) will be used for the calculation of PK parameters. The actual collection times will be used for evaluation of PK data. The Linear Up Log Down method (equivalent to the Linear Up/Log Down option in WinNonlin® Professional) will be used in the computation of AUCs.

The  $\lambda_z$  will not be presented for subjects who do not exhibit a terminal elimination phase in their concentration-time profiles. In order to estimate the first-order terminal elimination constant,  $\lambda_z$ , linear regression of the OP-101 concentration in logarithm scale vs. time will be performed using at least 3 data points. Uniform weighting will be selected to perform the regression analysis to estimate  $\lambda_z$ .

The constant  $\lambda_z$  will not be assigned if one of the following happens:

1.  $T_{max}$  is equals to one of the 3 last data points,
2. The adjusted regression coefficient (adjusted R-squared) is less than 0.8,
3. The percent of  $AUC_{0-inf}$  extrapolated exceeds 20%,
4. The estimated elimination rate indicates a positive slope, or
5. The terminal elimination phase is not linear (as appears in a semi-logarithmic scale) based on visual inspection.

In cases where the constant  $\lambda_z$  is not assigned, the values of associated variables (i.e.,  $T_{1/2}$ ,  $AUC_{0-inf}$ ,  $CL/F$ , and  $V_z/F$ ) may not be calculated.

PK parameters will be calculated based on PK Concentration Set.

### ***7.3.4 Pharmacokinetic Parameters Summary and Analysis***

The Plasma PK parameters will be summarized descriptively by treatment based on the PK

Parameter Population, including:  $C_{max}$ ,  $T_{max}$ ,  $T_{1/2}$ ,  $AUC_{0-last}$ ,  $AUC_{0-inf}$ ,  $CL/F$ ,  $V_z/F$ ,  $AUC_{0-48}$ , Geometric Mean [GM]), and CV% GM will also be calculated for  $C_{max}$  and AUCs.

The urine PK parameters such as  $Ae_{0-48}$ ,  $Fe_{0-48}$  and  $CL_r$  will be calculated and summarized descriptively.

#### 7.4 Safety Analyses

Safety analyses will be performed based on the Safety Population. Safety will be evaluated through assessments of AEs, treatment emergent adverse events (TEAE), vital signs, physical examinations, clinical laboratory tests.

##### 7.4.1 Adverse Events

An AE is defined as any untoward medical occurrence in a patient or clinical investigation subject administered a pharmaceutical product and which does not

necessarily have a causal relationship with this treatment. Therefore, AEs include:

- the onset of new signs, symptoms, conditions, and illnesses;
- exacerbation of pre-existing conditions or illnesses;
- abnormal laboratory findings deemed clinically significant by the Investigator;
- physical examination changes deemed clinically significant by the Investigator; and
- Abnormal medical evaluation findings (e.g., ECG) that are not documented at the Screening Visit and/or, in the Investigator's opinion, represent a clinically significant change in the subject's health during study participation. Screening medical evaluation findings that were not previously provided as medical history, and can be determined as starting prior to the Screening Visit, are not considered AEs and will be recorded as medical history.

Adverse events will be coded using a latest version of Medical Dictionary for Regulatory Activities (MedDRA) Version 21.0.

The Investigator will assess the severity (intensity) of each adverse event as mild, moderate, or severe, and will also categorize each adverse event as to its potential relationship to study drug using the categories of yes or no.

The severity of all adverse events should be graded according to the Common Terminology Criteria for Adverse Events (CTCAE) Version 4.0. These criteria can be found at <http://ctep.cancer.gov/reporting/ctc.html>. For those adverse events not listed in the CTCAE, the following grading system should be used:

- Mild (CTCAE Grade 1): Transient symptoms, awareness of sign/symptom, but easily tolerated and no interference with subject's daily activities.

- Moderate (CTCAE Grade 2): Marked signs/symptoms that interfere with subject's usual activities, but still acceptable.
- Severe (CTCAE Grade 3): Incapacitating signs/symptoms which cause considerable interference with the subject's daily activities, unacceptable.
- Life-threatening (CTCAE Grade 4): Life threatening or disabling adverse event.
- Death (CTCAE Grade 5): Death-related adverse event.

The relationship of an adverse event to the administration of the study drug is to be assessed according to the following definitions:

No (unrelated, not related, no relation) – The time course between the administration of study drug and the occurrence or worsening of the adverse event rules out a causal relationship and another cause (concomitant drugs, therapies, complications, etc.) is suspected.

Yes (related) – The time course between the administration of study drug and the occurrence or worsening of the adverse event is consistent with a causal relationship and no other cause (concomitant drugs, therapies, complications, etc.) can be identified.

The definition implies a reasonable possibility of a causal relationship between the event and the study drug. This means that there are facts (evidence) or arguments to suggest a causal relationship.

The following factors should also be considered:

- The temporal sequence from study drug administration- The event should occur after the study drug is given. The length of time from study drug exposure to event should be evaluated in the clinical context of the event.
- Underlying, concomitant, intercurrent diseases- Each report should be evaluated in the context of the natural history and course of the disease being treated and any other disease the subject may have.
- Concomitant drug- The other drugs the subject is taking or the treatment the subject receives should be examined to determine whether any of them might be recognized to cause the event in question.
- Known response pattern for this class of study drug- Clinical and/or preclinical data may indicate whether a particular response is likely to be a class effect.
- Exposure to physical and/or mental stresses- The exposure to stress might induce adverse changes in the recipient and provide a logical and better explanation for the event.
- The pharmacology and pharmacokinetics of the study drug-The known pharmacologic properties (absorption, distribution, metabolism, and excretion) of the study drug should be considered.

The investigator will record the action taken and outcome for each AE according to the following:

Action Taken

- Dose not changed;
- Drug Interrupted;
- Drug withdrawn;
- Not applicable;
- Other (specify); or
- Unknown

Outcome

- Fatal;
- Not recovered or not resolved;
- Recovered or resolved;
- Recovered or resolved with sequelae;
- Recovering or resolving; or
- Unknown.

**7.4.1.1 Serious Adverse Events**

An SAE is any AE occurring at any dose that results in any of the following outcomes:

- Death;
- Is life-threatening;
- Requires inpatient hospitalization or prolongs existing hospitalization;
- Persistent or significant incapacity or substantial disruption of the ability to conduct normal life functions; or
- Congenital anomaly/birth defect.

An important medical event that may not result in one of the above serious outcomes may be considered an SAE when, based upon appropriate medical judgment, it may jeopardize the subject or may require medical or surgical intervention to prevent one of the listed serious outcomes. Examples of such medical events include allergic bronchospasm requiring intensive treatment in an emergency room or at home, blood dyscrasias, or convulsions that do not result in inpatient hospitalization, or development of drug dependency or drug abuse.

#### ***7.4.1.2 Treatment-Emergent Adverse Event***

A TEAE is defined as an AE that emerges, having been absent prior to the study, or an AE that worsens in severity after the first dose of the study drug. Subjects reporting more than one adverse event for a given MedDRA preferred term will be counted only once for that term using the most severe incident. Subjects reporting more than one type of event within a system organ class (SOC) will be counted only once for that SOC. Safety population will be used for all the safety analysis.

TEAEs will be summarized by SOC and preferred term (PT) for each treatment and overall. The number and percentage of subjects experiencing TEAEs will be tabulated. Specifically, the following summaries will be presented:

- Overall summary of TEAEs by treatment and overall, with a breakdown by AE grading;
- TEAEs by SOC and PT by treatment;
- TEAEs by SOC, PT, and relationship to the study drug by treatment;
- TEAEs by SOC, PT, and maximum severity by treatment; and
- TEAEs by SOC, PT, maximum severity, and the relationship to the study drug by treatment.

Separate listings will be prepared for SAEs, AEs leading to deaths, and AEs leading to study discontinuation.

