9.2.3.1 Adverse events

Adverse events will be summarized overall and by system organ class and preferred term, and the relationship to the study drug received. A list of subjects who have SAEs and who discontinue from the study due to an adverse event will be provided. Deaths due to adverse events will also be provided.

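### The most-severe-incident counting rule in SAP 7.4.1.2, applied as written to the relationship table, classifies a subject by severity and so can count a subject with a related event as not related

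*SAP*

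**What the plan says.** Protocol 9.2.3.1 requires a breakdown by causality but gives no counting rule: "Adverse events will be summarized overall and by system organ class and preferred term, and the relationship to the study drug received".

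The SAP supplies the rules in 7.4.1.2. The unit is the subject: "The number and percentage of subjects experiencing TEAEs will be tabulated". A subject with repeat events of one PT "will be counted only once for that term using the most severe incident". For the system organ class the text is shorter: "Subjects reporting more than one type of event within a system organ class (SOC) will be counted only once for that SOC". It does not say which event supplies the severity or the causality.

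Five summaries follow. Two use causality: the third, "TEAEs by SOC, PT, and relationship to the study drug by treatment", and the fifth, "TEAEs by SOC, PT, maximum severity, and the relationship to the study drug by treatment". The second (incidence) and the fourth (maximum severity) do not. The first is an overall summary broken down by grade, and the SAP does not say that it includes a count of subjects with any related event.

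Causality is judged event by event. Under SAP 7.4.1 the investigator "will also categorize each adverse event as to its potential relationship to study drug using the categories of yes or no". Two events of one PT in one subject can therefore carry different answers.

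On listings, SAP 7.4.1.2 says: "Separate listings will be prepared for SAEs, AEs leading to deaths, and AEs leading to study discontinuation". It names no listing of all adverse events.

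**The concern.** Choosing the most severe incident is right for a table of severity. In a table of causality it is the wrong selector, because it picks an event on one attribute and then reports another. If the picked event is unrelated, a related event of the same PT in the same subject does not reach that subject's PT count.

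Safety and tolerability are the primary objective, and the protocol specifically asks for adverse events by relationship. Each cohort has four subjects, so one reclassified subject visibly changes a percentage. A mild, non-serious related event displaced in this way is also not recovered by any adverse event listing that the SAP names.

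**Working it through.** The plan gives no figure to reproduce, so the check applies the rule literally and counts.

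**Inputs.** One count per subject per PT, taken from the most severe incident (SAP 7.4.1.2). Causality yes or no for each event (SAP 7.4.1). Four subjects per cohort and up to eight in all (SAP 6.1).

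**Step 1: one subject, one PT, one related and one unrelated event, each Grade 1 to 3.** There are 3 × 3 = 9 pairings. The cells show how the subject is classified under the stated rule.

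| | Unrelated Grade 1 | Unrelated Grade 2 | Unrelated Grade 3 |
|---|---|---|---|
| **Related Grade 1** | undefined (tie) | not related | not related |
| **Related Grade 2** | related | undefined (tie) | not related |
| **Related Grade 3** | related | related | undefined (tie) |

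Three pairings are counted as related, three as not related, and three are undefined because the SAP has no tie-break. If a subject counts as related whenever any event of the PT is related, all nine are related. These are counts of possible cases, not probabilities.

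**Step 2: direction.** Under the stated rule a subject is counted as related only if the most severe event is related, and such a subject always has at least one related event. The subjects counted as related are thus a subset of those who had a related event of the PT. The rule can lower that number and cannot raise it.

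**Step 3: size per masked subject.** For the PT concerned, 1/4 = 25 percentage points in a cohort and 1/8 = 12.5 points across both cohorts. The cohort figure falls from 25% to 0% only if no other subject in that cohort has a related event of the same PT.

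**Step 4: what does not change.** The subject still appears once under the PT in the incidence table, and at the true maximum grade in the severity table. Only the attribution can be wrong.

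**Step 5: frequency.** The documents give none. As a pure assumption, let q be the chance that a given subject has such a masked pair. The chance of at least one masked subject among n is 1 − (1 − q)^n.

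- q = 1%: 1 − 0.99^4 = 4% for n = 4, and 1 − 0.99^8 = 8% for n = 8.
- q = 10%: 1 − 0.90^4 = 34% for n = 4, and 1 − 0.90^8 = 57% for n = 8.

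The width of this range shows only that the frequency is unknown, and the conclusion does not rest on it.

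**The case against.** The best defence is that the SAP is incomplete here rather than wrong. The rule could be read as operating within each relationship category, and SAP 1 and 8.2 place table specifications in a separate document that may settle the matter. The second part is a fair caution, since that document was not available for this review. But the SAP sentence is general, stands ahead of all five summaries, and neither states nor points to a different convention for causality. A programmer who follows it would produce the misclassification.

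Several other objections stand and limit the point:

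- **SOC row.** A reader might infer that the related event is absent from every row. The most-severe selector is written for the PT only. At SOC level the outcome is undefined, not shown to be lost.
- **Fifth table.** Showing the most severe event with its own causality is a coherent reading of that table's title. The clear misfit is in the third table. The fifth needs a definition.
- **Stopping and escalation.** A reader might infer that masking could hide a stopping trigger. Protocol 3.2 acts on drug-related events in a cohort and is not stated to use these tables, and escalation rests on safety review committee review (Protocol 3.1). Any mismatch would be in reporting.
- **Rarity.** The pair needs repeat events of one PT in one subject, discordant causality, and the unrelated event more severe. Protocol 5.2 reports no clinical adverse events at the higher intravenous doses, so such pairs may be uncommon after one subcutaneous dose. The event also remains on the eCRF.

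**Conclusion.** The point holds in a limited form. SAP 7.4.1.2 states one selector for repeat events, and for the table by relationship it is the wrong one. Applied as written, it counts some subjects with a related event as not related, leaves equal grades unresolved, and gives the SOC row no selector.

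The error runs in one direction, and each masked subject is worth 25 percentage points for that PT in a cohort of four. This assumes that the literal reading is followed, that the separate table specifications do not override it, and that the denominator is four.

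Two stronger conclusions are not supported. A reader might infer from the nine pairings that a related event is lost half of the time when the grades differ (3 of 6). That would need those pairings to be equally likely, and the documents say nothing on this. A reader might also infer that the whole safety profile is flattered, but overall incidence and maximum severity are not understated.

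The matter deserves correction because relationship to study drug is a required summary of the primary objective and the correction is nearly free. It does not threaten the conduct of the study.

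**What to change.** In SAP 7.4.1.2:

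- **Third summary (by relationship).** Count a subject once per PT and once per SOC, as related if any of that subject's TEAEs in that PT or SOC is related. This also resolves equal grades and the SOC row for this table.
- **Fifth summary (maximum severity and relationship).** Take the maximum severity within related TEAEs. Alternatively, state that the table shows the causality of the most severe event, and add a table of maximum severity among related events only.
- **Severity-only tables.** Keep the most-severe rule.

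Naming a listing of all adverse events would be a useful backstop.

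The core change is two sentences in the SAP and minor table programming. No new data are needed.

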#### ***7.4.2 Clinical Laboratory Tests***

The clinical laboratory tests will include Hematology and Coagulation, Chemistry, and Urinalysis at Screening and other time points as specified in Appendix Table 1.

Observed values from Baseline and each time point, as well as change from Baseline to each time point will be summarized descriptively based on Safety Population by Treatment. Baseline is defined as reading on Day -1 (Check-in). If the reading on Study Day -1 is missing, the last reading before dosing will be used as baseline. A summary table representing abnormal value of safety laboratory tests will also be presented. Additional Urinary biomarkers include albumin, creatinine, KIM-1, and NGAL will also be listed and summarized similarly.

Tests for HIV, HBsAg, and HCVab will be completed at the Screening Visit to determine eligibility. The data will be listed by treatment for Safety Population. Coagulation test including aPTT, PTT, INR will be completed at the Screening visit, and the data will be listed by treatment for the Safety Population.

An FSH test will be performed at Screening for women who are post-menopausal, with amenorrhea for at least 2 years.

#### **7.4.3 Vital Signs**

Vital signs included blood pressure, heart rate, respiratory rate, and temperature and will be taken after a 5-minute seated rest at Screening, Check-in, and other time points as specified in Appendix Table 1.

Observed values and change from baseline to each time point will be summarized descriptively by treatment based on Safety Population. Baseline is defined as reading at predose. If the reading at predose is missing, the last reading before dosing will be used as baseline.

The data for vital signs will be also listed based on the Safety Population.

#### **7.4.4 Physical Examination**

Complete physical examinations will be performed at screening, on Day -21 to -2, Day -1, Day 2, Day 3, Day 8 and Day 15, or at the Early Termination Visit. Body weight and height will be measured at screening and used to calculate BMI.

Physical examination data will be listed by treatment for the Safety Population.

#### **7.4.5 Pregnancy Test**

Serum and urine pregnancy test will be performed at Screening and Check-in. Data will be listed by visit and treatment for the Safety Population.

#### **7.4.6 Urine Drug Screen and Breath Alcohol Test**

Urine screen for drugs, cotinine screen and a breath alcohol test, will be performed at screening and on Study Day -1. Data will be listed by treatment for the Safety Population.

## **8 GENERAL REPORTING CONVENTIONS**

### **8.1 Statistical Software**

The creation of analysis datasets and all statistical analyses will be done using SAS® Version 9.4 or higher. Novotech standard operating procedures will be followed for the generation and validation of all programs and outputs.

Phoenix WinNonlin version 7.0 or higher will be used in the determination of the PK terminal phase and the calculation of PK parameters. All the PK parameters will also be calculated via SAS® and verified with the Phoenix WinNonlin results.

### **8.2 Format**

The format of tables, listings, and figures will be described in a stand-alone programming specifications document.

9 APPENDICES

Table 1: SCHEDULE OF PROCEDURES-Cohort 1 and 2

Study Procedure	Screening Period		Check-In	Treatment Period			Follow-Up Visits [1]		Early Termination Visit
	Days -21 to -2	Day -1		Day 1	Day 2	Day 3	Day 8	Day 15	
Informed consent	X								
Admit to investigational site		X							
Inclusion/exclusion criteria	X	X							
Medical history	X								
Demographics	X								
Prior/concomitant medications	X	X	X	X	X [3]		X	X	X
BMI calculation [2]	X								
Physical examination (complete)	X	X	X	X	X [3]		X	X	
Vital signs [4]	X	X	X	X	X [3]		X	X	X
Breath alcohol screen	X	X	X						
Pregnancy test [5]	X	X	X						
FSH [5]	X								
Urine drug and cotinine screen	X	X	X						
Safety laboratory tests (chemistry, hematology, and urinalysis) [6]	X	X	X	X	X [3]		X	X	X
aPTT, PTT, INR	X								
HIV, HBsAg, HCVab screen	X								
Plasma PK sampling [7]			X	X	X [3]				
Urine PK sampling [8]			X	X	X [3]				
Administer study drug [9]									
Assess adverse events	X	X	X	X	X [3]		X	X	X
Discharge from investigational site									

A 30-minute window for vital signs and all postdose procedures is allowed.

When multiple procedures are scheduled at the same time point, the order of procedures should be as follows: obtain vital signs, collect blood sample (drawn at nominal time), and obtain urine sample.

1. There will be a  $\pm 1$ -day visit window for Days 8 and 15.
  2. Body weight and height will be measured at screening and used to calculate BMI.
  3. Assessments will be performed prior to discharge.
  4. Vital signs (pulse rate, respiration rate, body temperature, and BP) will be recorded at all study visits after the subject has been seated or supine for  $\geq 5$  minutes. During the Treatment Period, vital signs will be measured predose, 30 and 60 minutes and at 2, 4, 12, 24 and 48 hours after SC dosing.
  5. A serum (beta HCG) pregnancy test will be performed at screening for female subjects of childbearing potential only. A urine pregnancy test will be performed at Day -1 for female subjects of childbearing potential only. A test for FSH level will be performed only for women of non-childbearing potential who are not surgically sterile.
  6. Safety laboratory tests will be performed under fasting conditions (at least 8 hours). Day 1 sample will be taken within 30 minutes prior to dosing. See Appendix B for the list of analytes assessed; eGFR will be assessed with each sample and will be based on the subject's creatinine level, age, sex, and race. KIM-1 and NGAL will be evaluated from urine collected on Day -1, Day 2, Day 3, Day 8, Day 15 and on Early Termination. Additional chemistry parameters (i.e., glycosylated haemoglobin and homocysteine) will only be assessed at screening.
  7. Plasma PK samples will be collected within 30 minutes prior to dosing, and at 30 min and 1, 2, 4, 6, 8, 10, 12, 16, 24, and 30-36 hours after SC injection, as well as on Day 3 ( $\sim 48$  hr). Blood samples for PK analysis can be obtained within  $\pm 5$  minutes of the scheduled sampling time for sample times  $\leq 12$  hours, within  $\pm 10$  minutes of the scheduled sampling time for sample times  $\leq 12$  hours, and within  $\pm 2$  hours of the scheduled sampling times for sample times  $> 12$  hours.
  8. Urine PK samples will be collected 60 to 30 minutes prior to dosing (spot sample) and between 0 to 4, 4 to 8, 8 to 12, 12 to 18, 18 to 24, and 24 to 48 hours after dosing.
  9. Cohort dosing will be separate and sequential. Dose escalation from Cohort 1 (4 mg/kg) to Cohort 2 (8 mg/kg) will be determined by the SRC after review of safety, tolerability up to Day 8, and any available PK data from Cohort 1.
- aPTT = activated partial thromboplastin time; BMI = body mass index; BP = blood pressure; eGFR = estimated glomerular filtration rate; FSH = follicle-stimulating hormone; HBV = hepatitis B virus; HCG = human chorionic gonadotropin; HCV = hepatitis C virus; HIV = human immunodeficiency virus; INR = international normalized ratio; PTT = partial thromboplastin time; SRC = safety review committee.

---

